
 To evaluate the efficacy of induction treatment with LY3471851 compared to placebo with respect to clinical, endoscopic, and histologic improvement 	
Secondary comparisons of interest are the difference between LY3471851 and placebo in the proportion of participants who have not permanently discontinued at Week 12 and have achieved at Week 12:
 
 clinical response endoscopic remission endoscopic response symptomatic remission symptomatic response histologic remission histologic-endoscopic mucosal healing 
Secondary comparisons with binary endpoints will use a composite estimand as described for the primary comparison.

Objectives	Estimands/Endpoints

 To evaluate the efficacy of maintenance treatment with LY3471851 compared to placebo with respect to clinical, endoscopic, and histologic improvement 	
Secondary comparisons of interest include the difference between LY3471851 and placebo in the proportion of participants who were responders at Week 12 (Week 12 Responders) and have not permanently discontinued at Week 52, who at Week 52 still have
 
 clinical remission clinical response endoscopic remission endoscopic response symptomatic remission symptomatic response histologic remission histologic-endoscopic mucosal healing 
Secondary comparisons with binary endpoints will use a composite estimand as described for the primary comparison.

 To evaluate the efficacy of treatment with LY3471851 compared to placebo with respect to patient-reported outcomes and quality of life measures 	
Comparison of mean changes from baseline to Week 12 and to Week 52 in scores for
 
 IBDQ Urgency NRS Abdominal Pain NRS Nocturnal Stools Bristol Stool Scale PGR-S Fatigue NRS 
Secondary comparisons with continuous endpoints will use a hypothetical efficacy estimand strategy to address the intercurrent events of early discontinuation to assess the effect of study treatment in a hypothetical trial where all participants have complete data and continue to take study treatment without discontinuing from the study.

 To evaluate the PK of LY3471851 	
 Week 12 LY3471851 trough concentrations

Objectives	Estimands/Endpoints
	

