This study does not include rescue therapy. Participants who are nonresponders at Week 12 will be assigned to the highest dose of LY3471851 (**CC1** µg), as described in Section 4.1. If these participants remain nonresponders at Week 26, they will be discontinued from study drug and enter post-treatment follow-up period (Section 7.1.1).

Corticosteroid tapering

Participants who enter the study on oral corticosteroid therapy for treatment of their UC should maintain the stable dose of corticosteroid during the entire 12-week induction period. Participants who achieve clinical response at Week 12 will initiate corticosteroid tapering, as described below. For participants who cannot tolerate the corticosteroid taper without recurrence of clinical symptoms, corticosteroid taper may be paused and/or corticosteroid dose may be increased up to the original dose at induction baseline (should not exceed induction baseline dose). In such cases, attempts to reinitiate corticosteroid tapering should be made within 2 weeks of interruption of taper, with a goal to complete tapering no later than Week 26.

Week 12 clinical nonresponders who undergo extended induction with the high dose of LY3471851 will begin corticosteroid tapering if clinical response is achieved at Week 26. For participants who cannot tolerate the corticosteroid taper without recurrence of clinical symptoms, corticosteroid taper may be paused and/or corticosteroid dose may be increased up to the original dose at induction baseline (should not exceed induction baseline dose). In such cases, attempts to reinitiate corticosteroid tapering should be made within 2 weeks of interruption of taper, with a goal to complete tapering no later than Week 40.

The recommended tapering schedule for oral corticosteroids (other than budesonide extended release tablets [budesonide MMX] or beclomethasone dipropionate [gastro-resistant prolonged release tablet]) is as follows.

Dose >10 mg/day prednisone or equivalent: taper daily dose by 5 mg/week until receiving 10 mg/day, and then continue tapering at 2.5 mg/week until 0 mg/day.

Dose ≤10 mg/day prednisone or equivalent: taper daily dose by 2.5 mg/week until 0 mg/day.

The recommended tapering schedule for participants receiving oral budesonide MMX 9 mg/day is to reduce tablets to 9 mg every other day for 2 weeks, followed by 9 mg every third day for 2 weeks, and then discontinue.

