The secondary clinical question of interest is: What is the intervention difference in IBDQ / Urgency NRS / Abdominal Pain NRS / Nocturnal Stools / Bristol Stool Scale / PGR-S / Fatigue NRS at Week 12 and Week 52 of intervention in patients with moderately to severely active UC regardless of intervention discontinuation for any reason and regardless of initiation of rescue intervention or change in background intervention?

The estimand is described by the following attributes:

Population: patients with moderately to severely active UC. Further details can be found in Section 3.

Endpoint: IBDQ / Urgency NRS / Abdominal Pain NRS / Nocturnal Stools / Bristol Stool Scale / PGR-S / Fatigue NRS at Week 12 and Week 52.

Treatment condition: the randomized treatment without rescue medication or change in background medication (treatment policy strategy). Further details on study interventions and concomitant, including rescue, interventions can be found in Section 6.

The 2 intercurrent events “intervention discontinuation for any reason” and “initiation of rescue intervention or change in background intervention “ are both addressed by the treatment condition of interest attribute. There are no remaining intercurrent events.

Population-level summary: difference in mean change in IBDQ / Urgency NRS / Abdominal Pain NRS / Nocturnal Stools / Bristol Stool Scale / PGR-S / Fatigue NRS at Week 12 and Week 52 between intervention conditions.

Rationale for estimand: The data collected after the treatment discontinuation or post-rescue medication will not represent the true efficacy effects.

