The randomization ratios are described in Section 1.2.1.

Study Periods

This study has multiple periods.

Screening period

This period begins with Visit 1, which occurs 5 weeks (or less) before the planned randomization visit. A participant's screening evaluations must be completed and reviewed to confirm the participant's eligibility before randomization and dosing occurs at Visit 2.

Blinded induction and blinded maintenance periods

The double-blind, placebo-controlled, 12-week induction treatment period begins at Visit 2. Dosing, sample collection, and assessments continue Q2W, as shown in the SOA in the protocol. Between Week 12 and Week 14, based on samples and assessments collected at Week 12, participants will be classified as either "Week 12 Responders" or "Week 12 Nonresponders" based on the "clinical response" criteria defined in the protocol.

- "Week 12 Responders" will continue to receive their same randomly assigned treatment throughout the blinded 40-week Maintenance Period, with the final dose occurring at Week 50 and the last maintenance assessments and sample collections at Week 52.
- "Week 12 Nonresponders" will enter the Extension Induction and Extension Maintenance Periods.

Extension induction and maintenance periods

Beginning at Week 14, participants who were classified as Week 12 Nonresponders will receive the high dose (CC1 μg) of LY3471851 Q2W, unless a lower dose is selected for Stage 2 based on interim analyses.

Between Week 26 and Week 28, based on samples and assessments collected at Week 26, these participants will again be classified according to their clinical response status based on MMS (responder or nonresponder).

- Participants who are classified as responders based on the samples and assessments at Week 26 will continue to receive LY3471851 Q2W as maintenance through the remainder of the study. These participants have their final dose at Week 50 and their last maintenance assessments and sample collections at Week 52.
- Participants who are classified as nonresponders based on the Week 26 samples and assessments will be permanently discontinued from study drug when his/her status as a nonresponder has been determined; such participants will enter the post-treatment follow-up period.

Post-treatment follow-up period

[figure not shown]

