4.1.2.2. Mixed-Effects Model for Repeated Measures

For the continuous secondary and exploratory efficacy and health outcome variables, MMRM analyses will be the main method to mitigate the impact of missing data. This approach assumes that missing observations are missing-at-random (missingness is related to observed data) during the study and takes into account both the missingness of data and the correlation of the repeated measurements.

All continuous endpoints will utilize MMRM to patients who permanently discontinued study drug or who were rescued.

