4.6.1. Extent of Exposure

Duration of exposure to study treatment (defined as time since first injection of study treatment in days) will be summarized by treatment group during the Induction Period, the Maintenance Period, and the Extension Period.

Duration of exposure during the Induction Period for the Safety Population will be calculated as:

(Disposition date (for those who have discontinued the Induction Period), OR Maintenance/Extension Start date -1 (for those who have completed the Induction Period), OR Date of last study visit in the Induction Period (for those who are still being treated in the Induction Period) – Date of first injection of study treatment + 1)

Duration of exposure during the Maintenance Period will be calculated as:

(Disposition date (for those who have discontinued the Maintenance Period), OR Date of last study visit in the Maintenance Period (for those who are still being treated in the Maintenance Period) – Date of the Visit 10 injection of study treatment + 1)

Duration of exposure to LY3471851 during the Extension Period will be calculated as:

(Disposition date (for those who have discontinued the Extension Period), OR Date of last study visit in the Extension Period (for those who are still being treated in the Extension Period) – Date of the Visit 10 injection of study treatment + 1)

Duration of exposure to LY3471851 for the combined Induction Period and Maintenance Period will be calculated as:

(Disposition date (for those who have discontinued the Maintenance Period), OR Date of last study visit in the Maintenance Period (for those who are still being treated in the Maintenance Period)– Date of first injection of LY3471851 + 1)

Duration of exposure to LY3471851 for the combined Induction Period and Extension Period will be calculated as:

(Disposition date (for those who have discontinued the Extension Period), OR Date of last study visit in the Extension Period (for those who are still being treated in the Extension Period)– Date of first injection of LY3471851 + 1)

The date of first injection of LY3471851 is defined in [Table KFAH.4](#)**Error! Reference source not found.**

Table KFAH.4. First Injection of LY3471851 by Treatment Group

	Visit of first LY3471851
All patients randomized to LY3471851 (regardless of Week 12 response status)	Week 0 (Visit 2)
Week 12 Inadequate Responders originally randomized to placebo and assigned to LY3471851 at Visit 10	Week 14 (Visit 10)

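### The SAP incidence-rate rule does not stop at the Week 14 switch to LY3471851, and the Week 52 PRO estimand leaves the handling of that switch unresolved

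*SAP*

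**What the plan says.** **The switch.** SAP Section 1.2 states: "Beginning at Week 14, participants who were classified as Week 12 Nonresponders will receive the high dose" (a lower dose may be chosen after the interim analyses). Table KFAH.4 in SAP Section 4.6.1 confirms that placebo patients are included. It lists "Week 12 Inadequate Responders originally randomized to placebo and assigned to LY3471851 at Visit 10" and dates their first active dose at Week 14.

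**Incidence rates.** SAP Section 4.6 adds up observation time within each treatment group. The clock starts at first dose. It ends at the event or, for patients without one, at the earlier of last dose plus 30 days and last visit. The between-group measure is the incidence rate difference. Sections 4.6.3.1 (infections of special interest) and 4.6.3.3 (malignancies) use this rule, the latter over the whole observation time. Nothing happens to the clock at Visit 10.

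**Week 52 PROs.** Item 3 of the secondary estimands in SAP Section 1.1 covers all patients. It names discontinuation and rescue or background change, and says that these "are both addressed by the treatment condition of interest attribute. There are no remaining intercurrent events". Its clinical question is posed "regardless of intervention discontinuation for any reason and regardless of initiation of rescue intervention or change in background intervention". Its rationale says that data after discontinuation or "post-rescue medication will not represent the true efficacy effects". SAP Section 4.4.2 analyses PROs in the ITT population, which Section 3 groups as assigned. Protocol Section 3 reads: "Secondary comparisons with continuous endpoints will use a hypothetical efficacy estimand strategy to address the intercurrent events of early discontinuation". Protocol Section 6.5 says: "This study does not include rescue therapy".

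**The concern.** A placebo nonresponder is on placebo for 14 weeks and then on active drug for up to 36 weeks of dosing. A rule that adds all of this time to the placebo group mixes the drug's own event rate into its comparator. The affected outcomes include serious and opportunistic infections, so a real signal against the extension dose could look smaller than it is. One purpose of the study is to characterise benefit and risk.

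For the PROs, the same patients may contribute Week 52 values while on LY3471851. The SAP neither clearly keeps nor clearly removes those values. Two analysts could follow the text in good faith and report different Week 52 differences.

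**Working it through.** **Person-time.** The plan gives no figure for this point. The inputs are:

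- Placebo group of about 40 (SAP Section 5).
- Switch at Week 14. Last dose at Week 50 for Week 12 responders and for Week 26 responders. Last dose taken as Week 26 for Week 26 nonresponders (SAP Section 1.2; Protocol Table 3).
- Clock end at last dose plus 30 days, which is 30/7 = 4.29 weeks. This comes before the follow-up visit, about 8 weeks after last dose.
- Assumptions not in the documents: placebo clinical response at Week 12, r = 20-40%; response at Week 26 after the switch, e = 20-60%; no dropout; events not allowed to shorten person-time. The 5% and 35% in SAP Section 5 are power assumptions for the primary endpoint, clinical remission, and do not supply these rates.

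Person-weeks before the switch = 40(1−r)×14 + 40r×54.29.

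Person-weeks after it = 40(1−r)e×40.29 + 40(1−r)(1−e)×16.29, where 40.29 = 54.29 − 14 and 16.29 = 26 + 4.29 − 14.

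Let p = after/(before + after).

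| r | e | before | after | p | 1−p |
|---|---|---|---|---|---|
| 0.2 | 0.20 | 882 | 675 | 0.433 | 0.567 |
| 0.2 | 0.35 | 882 | 790 | 0.472 | 0.528 |
| 0.2 | 0.60 | 882 | 982 | 0.527 | 0.473 |
| 0.4 | 0.20 | 1205 | 506 | 0.296 | 0.704 |
| 0.4 | 0.35 | 1205 | 592 | 0.330 | 0.670 |
| 0.4 | 0.60 | 1205 | 736 | 0.379 | 0.621 |

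**Effect on the rate difference, extension-dose arm.** Let L0 be the placebo rate and L1 the rate of the arm already on the extension dose. Assume both are constant and that switched patients take on L1. The tabulated difference is L1 − [(1−p)L0 + pL1] = (1−p)(L1 − L0). The table would show 1−p of the true difference, or 47-70%.

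**Dropout.** Suppose 20% stop in induction (mean last dose Week 6), and 20% of maintenance patients (last dose Week 32) and of extension responders (last dose Week 38) stop midway. At r = 0.2, e = 0.6:

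- before = 8×10.29 + 25.6×14 + 6.4×(0.8×54.29 + 0.2×36.29) = 765
- after = 25.6×0.6×(0.8×40.29 + 0.2×28.29) + 25.6×0.4×16.29 = 749
- p = 0.495

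At r = 0.4, e = 0.2 the same steps give p = 0.284. The share shown is then about 50-72%. If the induction dropouts are instead counted among the nonresponders, it is about 54-77%.

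**Effect on other arms.** A lower-dose arm with rate Ld also has nonresponders who change dose, for a share q of its person-time. The tabulated difference is [(1−q)Ld + qL1] − [(1−p)L0 + pL1]. Its error is q(L1 − Ld) − p(L1 − L0), which can be negative or positive. The 1−p result does not apply in general.

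**PRO text.** No arithmetic settles this part. The relevant texts are:

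- SAP 1.1, treatment condition: randomised treatment without rescue, labelled treatment policy.
- SAP 1.1, question: data wanted whatever happens after discontinuation or rescue.
- SAP 1.1, rationale: such data do not reflect the effect.
- SAP 4.1.2.2: "All continuous endpoints will utilize MMRM to patients who permanently discontinued study drug or who were rescued", without saying whether later values are kept.
- Protocol 3 and 9.4.1.2: hypothetical strategy, with patients continuing study treatment.
- SAP 1: no changes to the protocol analyses.

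The switch fits neither named event cleanly. The patient still receives study drug, and the protocol has no rescue therapy.

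**The case against.** **A split by period may be intended.** SAP Section 3 refers maintenance and extension analyses to a corresponding enrolled population, and exposure, laboratory, vital-sign and compliance summaries are by period. This stands as evidence of intent. But the table it points to defines no such population, Section 4.6 does not use one for incidence rates, and Section 4.6.3.3 asks for overall observation time.

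**A reader might infer that the SAP plans to count on-drug PRO values as placebo.** The documents do not support that. A placebo patient moved to LY3471851 has arguably left the randomised treatment. The protocol's hypothetical strategy and the SAP's own rationale both favour setting later values aside. The clinical question points the other way, and the SAP does not choose. The share of placebo-arm Week 52 values collected on LY3471851 would not measure bias either, because the MMRM also uses earlier visits and patients missing at Week 52.

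**A reader might apply 47-70% to every dose comparison.** The lower-dose algebra above shows why that fails.

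**Rates will be imprecise anyway.** Total placebo-labelled time across the grid is about 30-37 person-years (1557/52.18 to 1941/52.18). At an assumed 2-5 events per 100 person-years, that is about 0.6 to 1.9 events. The dated infection listing and the medical review of malignancies keep cases visible. This limits the consequence but does not justify a mislabelled denominator.

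**Conclusion.** The safety part holds on the text: the stated rule credits on-drug time and events of placebo nonresponders to placebo. Its existence needs no assumption; its size does. Under the assumed response rates, 30-53% of placebo-labelled person-time is affected without dropout. The difference against the arm already on the extension dose shrinks to 47-70% of its true value, given constant rates and full uptake of that arm's rate. For lower-dose arms neither size nor direction is fixed.

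The PRO part is narrower. The switch is unnamed and the estimand text contradicts itself, so the handling of post-switch Week 52 values is unresolved. No PRO bias is quantified.

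The Week 12 primary endpoint precedes the switch, and the Week 52 binary endpoints are limited to Week 12 responders (SAP Section 4.4.1.3). Neither is affected. This should be fixed, but it does not threaten the main conclusion.

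**What to change.** 1. **SAP Sections 4.6 and 4.6.3.3.** Report rates and differences by randomised arm, stopping time and events at the Visit 10 dose for every nonresponder whose treatment or dose changes there. Either keep the time of nonresponders already on the extension dose, since nothing changes for them, or compare all arms over induction only, up to Visit 10. Report extension time separately as LY3471851. Cost: one derived date and extra tables; fewer placebo person-years, and after Week 14 the placebo time comes only from responders.
2. **SAP Section 1.1, item 3.** Name the switch as an intercurrent event. In line with the protocol's hypothetical strategy, exclude post-switch PRO values from the MMRM for patients whose treatment changes at Visit 10. Reconcile the question, treatment condition and rationale. Summarise extension PROs separately. Cost: the Week 52 comparison leans more on missing-at-random.
3. **SAP Section 3.** Define the maintenance and extension populations, and say whether the original randomisation or the Visit 10 allocation governs grouping in each analysis.

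No new data are needed.

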1.2. Study Design

Study KFAH is an adaptive Phase 2 multicenter, randomized, double-blind, placebo-controlled, parallel-group study to evaluate the efficacy and safety of multiple dose levels of LY3471851 in adult patients with moderately to severely active UC. Enrolled study participants will have either

- an inadequate response to, loss of response to, or be intolerant to corticosteroid or immunomodulator therapy for UC (termed “conventional-failed”), or
- an inadequate response to, loss of response to, or are intolerant to biologic or JAK inhibitor therapy for UC (termed “advanced therapy-failed”).

Study Stages

This adaptive study has two stages.

Stage 1: Approximately 100 participants will be randomly assigned to one of three treatment groups, including placebo. Interim analyses will be conducted for safety, dosing tolerability, and efficacy. These interim analyses will determine the doses to be used in Stage 2.

Note: Participants enrolled during Stage 1 of the study will remain on their randomly assigned Stage 1 doses. Their doses will be changed only if necessary due to safety reasons or due to their clinical response status at the end of Stage 1.

Stage 2: Approximately 100 additional study participants will be enrolled and randomly assigned to study treatment groups as well as placebo. The treatment doses used in Stage 2 may include any of the doses used in Stage 1, as well as one or more additional LY3471851 doses, not exceeding 1800 µg. The Stage 2 LY3471851 treatment doses will be determined by the sponsor based on results of the Stage 1 interim analyses and recommendations of the sponsor’s IAC. A small group of sponsor personnel having pre-identified roles and no contact with investigative sites may review the IAC recommendation and may also review unblinded data in order to further assess the recommendation. The IAC charter that describes the process for internal decision-making and action plan will be provided.

Thus, whereas Stage 1 will have three treatment groups (including placebo), Stage 2 could have more treatment groups or fewer (including placebo).

The sponsor intends for the transition from Stage 1 to Stage 2 to be seamless, with participant screening and enrollment activities occurring continuously in the transition period. The study IWRS will allocate newly enrolling participants to groups according to the Stage 1 randomization ratio until the Stage 2 groups have been decided upon and implemented.

The randomization ratios are described in Section 1.2.1.

Study Periods

This study has multiple periods.

Screening period

This period begins with Visit 1, which occurs 5 weeks (or less) before the planned randomization visit. A participant's screening evaluations must be completed and reviewed to confirm the participant's eligibility before randomization and dosing occurs at Visit 2.

Blinded induction and blinded maintenance periods

The double-blind, placebo-controlled, 12-week induction treatment period begins at Visit 2. Dosing, sample collection, and assessments continue Q2W, as shown in the SOA in the protocol. Between Week 12 and Week 14, based on samples and assessments collected at Week 12, participants will be classified as either "Week 12 Responders" or "Week 12 Nonresponders" based on the "clinical response" criteria defined in the protocol.

- "Week 12 Responders" will continue to receive their same randomly assigned treatment throughout the blinded 40-week Maintenance Period, with the final dose occurring at Week 50 and the last maintenance assessments and sample collections at Week 52.
- "Week 12 Nonresponders" will enter the Extension Induction and Extension Maintenance Periods.

Extension induction and maintenance periods

Beginning at Week 14, participants who were classified as Week 12 Nonresponders will receive the high dose (CC1 μg) of LY3471851 Q2W, unless a lower dose is selected for Stage 2 based on interim analyses.

Between Week 26 and Week 28, based on samples and assessments collected at Week 26, these participants will again be classified according to their clinical response status based on MMS (responder or nonresponder).

- Participants who are classified as responders based on the samples and assessments at Week 26 will continue to receive LY3471851 Q2W as maintenance through the remainder of the study. These participants have their final dose at Week 50 and their last maintenance assessments and sample collections at Week 52.
- Participants who are classified as nonresponders based on the Week 26 samples and assessments will be permanently discontinued from study drug when his/her status as a nonresponder has been determined; such participants will enter the post-treatment follow-up period.

Post-treatment follow-up period

[figure not shown]
All participants will have a post-treatment follow-up visit (Visit 801) for safety assessments. Visit 801 occurs approximately 6 weeks after the Week 52 visit. The last dose of study drug is given at Week 50. Thus, participants will have been withdrawn from study drug for approximately 8 weeks at Visit 801. Participants who were positive for anti-HBc at screening will have one additional post-treatment follow-up visit (Visit 802).

Early discontinuation

Participants who permanently discontinue the study drug early or withdraw from the study will undergo early termination procedures, including an ETV and the post-treatment follow-up visits specified in the SoA.

[Figure KFAH.1](#) and [Figure KFAH.2](#) show the study design.

[figure not shown]
Trial Schema

Abbreviations: D = day; DNA = deoxyribonucleic acid; ETV = early termination visit; HBV = hepatitis B virus; LY= LY3471851; Q2W = every 2 weeks; W = Week; w = weeks.

Figure KFAH.1. Study Schematic (Induction and Maintenance Periods)

Nonresponder Schema

Abbreviations: DNA = deoxyribonucleic acid; ETV = early termination visit; HBV = hepatitis B virus; Q2W = every 2 weeks; W = Week; w = weeks.

Note: The extension dose could be lower than CCI µg LY3471851, based on interim analyses.

Figure KFAH.2. Study Schematic (Nonresponder Extension Periods)

